5.4.8 Long-term Grooved Pegboard

Mean change from baseline in the time (seconds) to complete the Grooved Pegboard, with the non-dominant hand, at 12 months after the first dose of IMP.

Baseline is defined as the time of administration of the first dose of IMP (Day 1, Cycle 1).

Analysis of Covariance. Long-term grooved pegboard will be analysed by Analysis of Covariance (ANCOVA) using the baseline value as a continuous covariate and study (POLAR-A / POLAR-M), region (Asia / non-Asia) and treatment as factors. Least square means and its corresponding 95% confidence intervals will be presented.

Data presentations

- Table: ANCOVA analysis - Number of patients (N), Point Estimate (LSM), 95% CI and P-value by treatment group/treatment comparison (PledOx 5 µmol/kg vs Placebo).
- Table: descriptive statistics of observed values by treatment and total for each treatment cycle.
- Table: descriptive statistics of change from baseline by treatment and total for each treatment cycle.
- Figure: shift plot (using jitter) of baseline vs 12-month assessment visit.

All observed values of Grooved Pegboard will also be listed by patient.

5.4.9 Long-term Pain (NRS)

Mean change from baseline in worst pain in hands or feet in the past week, using a NRS, at 12 months after the first dose of IMP. NRS is measured on an ordinal scale 0-10.

Baseline is defined as the time of administration of the first dose of IMP (Day 1, Cycle 1).

Analysis of Covariance. Long-term pain will be analysed by Analysis of Covariance (ANCOVA) using the baseline value as a continuous covariate and study (POLAR-A / POLAR-M), region (Asia / non-Asia) and treatment as factors. Least square means and its corresponding 95% confidence intervals will be presented.

Data presentations

- Table: ANCOVA analysis - Number of patients (N), Point Estimate (LSM), 95% CI and P-value by treatment group/treatment comparison (PledOx 5 µmol/kg vs Placebo).
- Table: descriptive statistics of observed values by treatment and total for each treatment cycle.
- Table: descriptive statistics of change from baseline by treatment and total for each treatment cycle.
- Figure: shift plot (using jitter) of baseline vs 12-month assessment visit.

All observed values of worst pain in hands or feet will also be listed by patient.

5.4.10 Change in Pain (NRS)

The proportion of patients with a 2-point, 3-point and 4-point increase vs baseline in worst pain in hands or feet in the past week using NRS at 9 and 12 months after the first dose of IMP.

Baseline is defined as the time of administration of the first dose of IMP (Day 1, Cycle 1).

Exact Logistic Regression. The proportion of patients with a 2-point, 3-point and 4-point increase from baseline in worst pain in hands or feet will be analysed by an exact logistic regression model adjusted for study (POLAR-A / POLAR-M) and region (Asia / non-Asia). Estimate of the treatment effect and its corresponding 95% confidence interval will be based on the odds-ratio.

Data presentations

- Table: number and percentage of patients having a 2-point, 3-point and 4-point increase in worst pain in hands or feet based on the exact logistic regression model will be presented by number of patients (N), number of patients (%) with 2-point, 3-point and 4-point increase in worst pain in hands or feet at 9 and 12 months after first doses of IMP, respectively for each treatment group, and odds-ratios, 95% CIs and p-values for the treatment comparisons.

All values will also be listed by patient.

The analyses will be based on the observed cases. Hence, no imputation of missing values will be done.

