5.3.5 Pain (NRS)

Mean change from baseline in worst pain in hands or feet in the past week, using a numerical rating scale (NRS), at 9 months after the first dose of IMP. NRS is measured on an ordinal scale 0-10.

Baseline is defined as the time of administration of the first dose of IMP (Day 1, Cycle 1).

Analysis of Covariance. Pain will be analysed by Analysis of Covariance (ANCOVA) using the pain baseline value as a continuous covariate and study (POLAR-A / POLAR-M), region (Asia / non-Asia) and treatment as factors. Least square means and its corresponding 95% confidence intervals will be presented.

Data presentations

- Table: ANCOVA analysis - Number of patients (N), Point Estimate (LSM), 95% CI and P-value by treatment group/treatment comparison (PledOx 5 µmol/kg vs Placebo).
- Table: descriptive statistics of observed values by treatment and total for each treatment cycle.
- Table: descriptive statistics of change from baseline by treatment and total for each treatment cycle.
- Figure: shift plot (using jitter) of baseline vs 9-month assessment visit.

All observed values of worst pain in hands or feet will also be listed by patient.

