5.4 Exploratory Endpoints

5.4.1 Any CIPN

Any CIPN is defined as the proportion of patients with any CIPN scoring 1, 2, 3 or 4, in any of the first 4 items of the FACT/GOG-NTX-13 (i.e. FACT/GOG-NTX-4), targeting numbness, tingling or discomfort in hands and/or feet, at all other timepoints after the first dose of IMP.

Baseline is defined as the time of administration of the first dose of IMP (Day 1, Cycle 1).

Any CIPN will derived (SAS) as follows:

```
cipn3=0;  
IF ntx1_std=. AND ntx2_std=. AND ntx3_std=. AND ntx4_std=. THEN cipn3=.;  
ELSE IF ntx1_std IN('1','2','3','4') OR ntx2_std IN('1','2','3','4') OR  
      ntx3_std IN('1','2','3','4') OR ntx4_std IN('1','2','3','4') THEN  
cipn3=1;
```

Data Presentations

- Table: the number and percentage of patients with Any CIPN along with its 95% CI presented by treatment group and total for each treatment visit/assessment visit. The confidence intervals will be based on the method of Clopper-Pearson (exact)
- Figure: the proportion (including 95% CIs) of patients with Any CIPN will be graphically depicted (lineplot) vs treatment cycle/assessment visit by treatment group.
- All observed values of Any CIPN will be listed by patient

The analysis of Any CIPN will be based on observed cases. Hence, no imputation of missing values will be done.

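### The models for 2-, 3- and 4-point pain increases (SAP 5.4.10) leave out baseline pain as a covariate and so give up a little precision on an exploratory endpoint

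*SAP*

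**What the plan says.** Section 5.4.10 of the SAP defines the endpoint as "The proportion of patients with a 2-point, 3-point and 4-point increase vs baseline in worst pain in hands or feet", assessed at 9 and at 12 months. Three thresholds at two visits give six binary comparisons. Each "will be analysed by an exact logistic regression model adjusted for study (POLAR-A / POLAR-M) and region (Asia / non-Asia" factors, with an odds ratio, 95% CI and p-value, on observed cases. Baseline is the Day 1, Cycle 1 value. It does not appear on the right-hand side of the model.

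The same scale is modelled in two other places:

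- Section 5.3.5 (9 months, secondary): "Pain will be analysed by Analysis of Covariance (ANCOVA) using the pain baseline value as a continuous covariate".
- Section 5.4.9 (12 months, exploratory): "Long-term pain will be analysed by Analysis of Covariance (ANCOVA) using the baseline value as a continuous covariate".

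Section 3 sets the general rule that analyses include study and region as stratification factors. It does not mention baseline values. Section 5.4.10 falls under "5.4 Exploratory Endpoints".

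**The concern.** A binary outcome built from a change score still depends on where the patient started. Subtracting baseline to form the change does not remove that dependence: patients with higher baseline pain tend to drift down, and the scale limits how far they can rise. Baseline pain is therefore a prognostic variable already in hand, and leaving it out of a logistic model costs some power.

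The omission also stands out within the SAP. Besides the two pain ANCOVAs, the other modelled change-from-baseline endpoints (cold sensitivity in 5.3.2, vibration in 5.3.4, pegboard in 5.3.6 and 5.4.8) all carry their baseline as a covariate. Where the SAP drops a baseline covariate from the primary CIPN analysis, Section 2.5 explains why: very few patients had CIPN at baseline. Section 5.4.10 offers no such explanation. At stake is the precision of six exploratory comparisons; no primary or secondary conclusion depends on them.

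**Working it through.** **1. The plan's own figure.** The SAP states no power, event rate or sample size for the pain-increase endpoints. Its only design figure is for the primary endpoint (Section 2.4): 112 per group, 40% vs 20%, two-sided 0.05, 91% power. With mean rate 0.30,

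z = [0.20 × √112 − 1.96 × √(2 × 0.30 × 0.70)] / √(0.40 × 0.60 + 0.20 × 0.80) = (2.117 − 1.270) / 0.632 = 1.338,

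which gives power 0.9096. The figure reproduces, but it has no bearing on this point.

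**2. Does baseline bear on the outcome?** The SAP states that "NRS is measured on an ordinal scale 0-10". A rise of k points is impossible when baseline exceeds 10 − k:

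| Rise | Impossible from a baseline above |
|---|---|
| 2 points | 10 − 2 = 8 |
| 3 points | 10 − 3 = 7 |
| 4 points | 10 − 4 = 6 |

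So baseline predicts the outcome in principle. How strongly depends on the baseline pain distribution, which the SAP does not give.

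**3. Plausible sample size.** Section 1 gives 301 patients randomised 1:1 in POLAR-A and 290 randomised 1:1:1 in POLAR-M. For 5 µmol/kg vs placebo combined, that is about 301/2 + 290/3 = 150.5 + 96.7 ≈ 247 per arm, before mITT exclusions and missing visits. The simulations below assume 118 to 200 per arm, which is under that ceiling.

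**4. Size of the loss.** These are simulations of logistic regression on treatment, with and without baseline pain. Baseline distribution, event rates and analysed numbers are all assumptions. The fits were not exact.

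| Assumed inputs | Result when baseline is added |
|---|---|
| 180 per arm; 50-85% at baseline 0, the rest 1-7; carry-over of baseline 0.3-0.6; event rate 18-29%; 1,500 runs in each of six scenarios; 2-point rise | Power up about 1 to 3.5 points (e.g. 54.5% to 58.0%, 61.1% to 62.5%) |
| 118 or 200 per arm; 50-90% at baseline 0; 1,000 runs per setting; Wald tests; study and region left out | Power changed by −0.5 to +5.9 points (e.g. 58.2% to 64.1% with 200 per arm and 50% at zero) |
| 180 per arm; 2-point and 4-point rises | Power up about 1 to 5 points (2-point) and 1 to 2.5 points (4-point) |

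Type I error in the second set was 0.038-0.065 without baseline and 0.041-0.060 with it. With 1,000 runs the Monte Carlo standard error at 5% is √(0.05 × 0.95 / 1000) = 0.007, so both ranges are about nominal. In the third set it was at or below about 5% either way. Many fits in the second set gave convergence warnings that were not traced to one model or the other, so its extremes should be read loosely.

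**5. The odds ratio.** In the second set the mean odds ratio moved from 0.54-0.62 unadjusted to 0.53-0.59 adjusted. Movement away from 1 is expected, because the odds ratio is non-collapsible: the adjusted value is a different, conditional quantity.

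**The case against.** The strongest reply is that nothing here is wrong. Section 5.4.10 does what Section 3 asks, and it matches the SAP's other exact logistic model, the exploratory CIPN analysis in Section 5.1.1. The SAP's pattern is coherent: continuous outcomes get ANCOVA with baseline, and binary outcomes get study and region. Baseline-adjusted analyses of the same scale already exist at both visits. No alpha and no power are attached to 5.4.10. Adding a many-valued covariate to an exact conditional analysis can make it heavy or degenerate, and no gain has been shown under the exact method itself.

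Most of this stands, and it limits the point to precision. Two parts are weaker. The CIPN model in 5.1.1 concerns a status at 9 months, not a rise from baseline, so the parallel is loose. And the ANCOVAs answer a different question from the responder proportions, so they do not restore the precision lost there.

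A reader might also infer more than the SAP supports:

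- *That the plan ignores baseline pain.* It does not: baseline is subtracted in forming the outcome. Only the covariate is absent.
- *That every other pain analysis adjusts for it.* Only the two NRS ANCOVAs do. The descriptive NRS tables and the EQ-5D-5L pain item (5.4.7) are unadjusted.
- *That the unadjusted odds ratio is biased towards 1* (0.56 vs 0.53 in one simulated case). That is non-collapsibility, not bias.
- *That the scale ceiling drives the loss.* In the first simulation baselines stop at 7, and a 2-point rise is blocked only from 9 or 10, so the ceiling played no part there.

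**Conclusion.** The point holds as a small improvement. Section 5.4.10 leaves out a collected, prognostic baseline value that both other modelled NRS pain analyses use, and it gives no reason. The planned comparison remains valid under randomisation and does not contradict the SAP. The cost is precision on an exploratory endpoint: between about 0 and 6 percentage points of power. That range rests on an assumed 118-200 patients per arm, an assumed 50-90% of patients with no baseline pain, and non-exact fits. If nearly all patients start at zero, baseline carries little information and the gain shrinks towards nothing.

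One qualification applies to the appeal to randomisation. The analysis uses observed cases in an mITT set that depends partly on post-baseline events (Section 3.1), so balance among those analysed is not guaranteed. Conditioning on baseline gives some protection, but its size was not assessed.

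**What to change.** In Section 5.4.10, add baseline worst-pain NRS (0-10) as a covariate alongside study and region, for all three thresholds at 9 and 12 months. Pre-specify the fallback if the exact fit is infeasible or degenerate: Firth or ordinary logistic regression with profile-likelihood confidence intervals. State that the odds ratio is conditional on baseline pain.

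If the sponsor prefers to keep the exact model as it is, the smaller alternative is to run the adjusted model as a sensitivity analysis, or to add one sentence saying why baseline is omitted.

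The edit is one covariate and a sentence or two, made before unblinding. It is not free: the exact method may have to be replaced, and the adjusted odds ratio can no longer be checked directly against the crude proportions in the same table.

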5.4.11 Health Economic Impact

Health economic impact, measured by the combined impact of medical resource utilization (hospitalizations, outpatient visits, medical procedures and medical use), patient impact (AEs, fall accidents, functional loss) and indirect societal costs (loss of ability to work), at 6 and 12 months after the first dose of IMP.

Baseline is defined as the time of administration of the first dose of IMP (Day 1, Cycle 1).

Data presentations

All health economic variables will be presented by summary statistics (including change from baseline where appropriate) by treatment group and total for each visit.

All observed values of health economic impact will also be listed by patient.

6. SAFETY EVALUATION

All safety evaluations will be performed on the safety analysis set unless specified otherwise.

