2.2.2 Secondary Objectives

The secondary objectives of the study are to compare each dose of PledOx vs placebo regarding the following:

Efficacy

- The proportion of patients with mild, moderate or severe chronic CIPN
- The sensitivity to touching cold items
- The cumulative dose of oxaliplatin during chemotherapy
- The vibration sensitivity on the lateral malleolus
- The worst pain in hands or feet
- The functional impairment (in the non-dominant hand)
- The sustained efficacy on prevention of CIPN during long-term follow-up

Safety

- Overall response rate (ORR)
- Progression-free survival (PFS)
- Overall survival (OS)
- Safety and tolerability

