3.1 Analysis Sets

The analysis set “All randomised patients (ITT)” consists of all patients who were assigned a randomisation number, irrespective of the treatment they received, if any.

The modified ITT (mITT) analysis set includes patients that fulfil at least one of the following criteria:

1. the patient was randomised prior to December 1, 2019 (ie the patient was eligible for at least 3 months of IMP) and had at least one post-baseline assessment for efficacy, or
2. the 3 month Assessment Visit occurred prior to 1 March, 2020, or
3. the patient received the 6th cycle of IMP after 1 March, 2020.

Patients will be analysed according to the treatment they are assigned to at randomisation, irrespective of what treatment they actually received.

The safety analysis set (SAF) consists of all randomised patients who receive at least one dose of IMP. Patients will be analysed according to the randomised study treatment actually received.

The list of patients to be included in each of the analysis sets is to be agreed between the project statistician and the Sponsor prior to unblinding, once all study data is available.

All enrolled patients will be listed indicating their membership to each analysis set along with the reason for exclusion.

The PK population (POLAR-M only) includes a subset of patients at pre-selected sites in all participating regions, where blood samples will be collected for pharmacokinetics and ECG assessments.

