6.10 Progression-Free Survival (POLAR-M only)

Endpoint. Progression-Free Survival (PFS) is defined as the time from the date of randomisation until the date of objectively determined PD (according to RECIST v1.1) or death due to any cause. Patients without objectively determined PD who are alive at the end of the follow-up period (or who were lost to follow up) will be censored on the date of the patient's last complete radiographic tumor assessment. If no baseline or post-baseline radiologic assessment is available, the patient will be censored at the date of randomisation.

Cox Proportional Hazards Model. Time (number of days) from randomisation to event or censoring will be analysed by a cox proportional hazards model using region (Asia / non-Asia) and Treatment as fixed factors in the model. The hazard ratio along with its 95% confidence interval of the PledOx doses compared to placebo will be estimated.

Data presentations

- Table: Progression-free survival based on the cox proportional hazards model will be presented by the number and percentage of events (N, %), Hazard Ratio (95% CI), Minimum, Q1, Median, Q3 and Maximum time to event or censoring by treatment group and total.
- Figure: Progression-free survival will be depicted graphically by a Kaplan-Meier plot by treatment group.

All PFS data will be listed by patient.

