6.11 Overall Survival (POLAR-M only)

Endpoint. Overall Survival (OS) is defined as the time from the date of randomisation until the date of death from any cause. If the patient was alive at the end of the follow-up period (or was lost to follow-up), the patient will be censored on the last date the patient was known to be alive.

Cox Proportional Hazards Model. Time (number of days) from randomisation to event or censoring will be analysed by a cox proportional hazards model using region (Asia / non-Asia) and Treatment as fixed factors in the model. The hazard ratio along with its 95% confidence interval of the PledOx doses compared to placebo will be estimated.

Data presentations

- Table: Overall survival based on the cox proportional hazards model will be presented by the number and percentage of events (N, %), Hazard Ratio (95% CI), Minimum, Q1, Median, Q3 and Maximum time to event or censoring by treatment group and total.
- Figure: Overall survival will be depicted graphically by a Kaplan-Meier plot by treatment group.

All OS data will be listed by patient.

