6.12 Disease-Free Survival (POLAR-A only)

Endpoint. Disease-Free Survival (DFS) is defined as the time from the date of randomisation until the date of objectively determined signs or symptoms of recurrence of Colorectal Cancer (CRC) or death due to any cause. Signs and symptoms may include any assessment result that, in the opinion of the Investigator, provides evidence for the recurrence of the disease. Patients without objectively determined disease recurrence who are alive at the end of the follow-up period (or who were lost to follow up) will be censored on the date of the patient's last assessment of disease recurrence. If no baseline or post-baseline radiologic assessment is available, the patient will be censored at the date of randomisation.

Cox Proportional Hazards Model. Time (number of days) from randomisation to event or censoring will be analysed by a cox proportional hazards model using region (Asia / non-Asia) and Treatment as fixed factors in the model. The hazard ratio along with its 95% confidence interval of PledOx 5 µmol/kg compared to placebo will be estimated.

Data presentations

- Table: Disease-free survival based on the cox proportional hazards model will be presented by the number and percentage of events (N, %), Hazard Ratio (95% CI), Minimum, Q1, Median, Q3 and Maximum time to event or censoring by treatment group and total.
- Figure: Disease-free survival will be depicted graphically by a Kaplan-Meier plot by treatment group.

All DFS data will be listed by patient.

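### PFS, OS and DFS are timed from randomisation but default to the safety set, which leaves out 9 of 591 randomised patients and groups the rest by treatment received

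*SAP*

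**What the plan says.** The analysis set for the three time-to-event endpoints follows from a chain of statements in the SAP.

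- Sections 2.1.2 and 2.2.2 list DFS (POLAR-A), and PFS and OS (POLAR-M), under the safety part of the secondary objectives.
- Section 6 sets the default: "All safety evaluations will be performed on the safety analysis set unless specified otherwise".
- Section 3.1 defines that set: "The safety analysis set (SAF) consists of all randomised patients who receive at least one dose of IMP". On grouping it adds: "Patients will be analysed according to the randomised study treatment actually received".
- Sections 6.10 to 6.12 start every clock at randomisation. For PFS: "Progression-Free Survival (PFS) is defined as the time from the date of randomisation until the date of objectively determined PD". For OS: "Overall Survival (OS) is defined as the time from the date of randomisation until the date of death from any cause". For DFS: "Disease-Free Survival (DFS) is defined as the time from the date of randomisation until the date of objectively determined signs or symptoms of recurrence". Each section specifies a Cox model with region and treatment, and none names an analysis set.
- Section 3.1 also defines an all-randomised (ITT) set, which "consists of all patients who were assigned a randomisation number, irrespective of the treatment they received, if any". Sections 6.10 to 6.12 do not call on it.

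Two further rules bear on the point. Sections 6.10 and 6.12 censor a patient at randomisation when no baseline or post-baseline radiologic assessment exists; Section 6.11 has no such rule. Section 2.5 limits statistical analyses to data within 12 months of the first IMP dose.

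**The concern.** Follow-up starts at randomisation, but entry to the analysis depends on something that happens later, namely receiving IMP. A patient who dies between randomisation and a planned first dose meets the OS definition and still cannot be counted. Grouping by treatment received is a second departure from the arms as allocated.

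These hazard ratios are the SAP's between-arm evidence on whether PledOx harms tumour control or survival. For that use, the comparison should keep the arms as randomised unless there is a reason not to, and the SAP gives none. The efficacy analyses in Section 5 use the mITT set, which Section 3.1 groups by assigned treatment. The survival endpoints are therefore grouped less strictly than the neuropathy endpoints.

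**Working it through.** **Counts.** The disposition table in Section 1 gives randomised and dosed patients. The SAP's totals reproduce: 301 + 290 = 591 randomised, and 297 + 285 = 582 dosed.

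| | Randomised | Dosed (safety set) | Left out |
|---|---|---|---|
| POLAR-A (DFS) | 301 | 297 | 4 (4/301 = 1.3%) |
| POLAR-M (PFS, OS) | 290 | 285 | 5 (5/290 = 1.7%) |
| Both | 591 | 582 | 9 (9/591 = 1.5%) |

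The SAP states no power or event count for PFS, OS or DFS, so there is no such figure to reproduce.

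**Precision.** Use power = Φ(√(d/4)·|ln HR| − 1.96), where d is the number of events in a two-arm contrast. Assume HR = 1.5 and, in POLAR-M, an event fraction of 50%. With 290/3 = 96.7 patients per arm, the ITT set gives d = 96.7 and power 0.513. The safety set gives d = 96.7 × 285/290 = 95.0 and power 0.506. At assumed event fractions of 10% to 70% the loss stays below one percentage point in both studies. Lost information is not the issue.

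**Bias, extreme cases for OS in POLAR-M.** Assume that the true HR is 1, hazards are exponential, all five undosed patients belong to one arm of n = 96.7, and a fraction f of each arm has died.

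- Hazard index in the full arm: −ln(1 − f).
- If all five died, the reduced arm has f₁ = (96.7f − 5)/91.7.
  - f = 20%: f₁ = 0.156, HR = 0.170/0.223 = 0.76.
  - f = 50%: f₁ = 0.473, HR = 0.640/0.693 = 0.92.
- If none of the five died, f₂ = 96.7f/91.7.
  - f = 20%: HR = 1.06.
  - f = 50%: HR = 1.08.
- If only one patient is undosed in that arm, and that patient died, the HR is about 0.95 at f = 20% and 0.985 at f = 50%.

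These are limits on assumed inputs, not estimates. The SAP gives no event fraction, no split of the undosed by arm, and no outcomes for them.

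**PFS and DFS.** If an undosed patient has no radiologic assessment, the rule in Sections 6.10 and 6.12 censors that patient at day 0. A patient with zero follow-up adds nothing to the Cox partial likelihood, so moving to the ITT set would leave the PFS and DFS estimates almost unchanged. Whether the nine lack assessments is not stated. OS has no such rule, so there the choice of set changes who can contribute.

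**Data limit.** Section 2.5 counts 12 months from the first IMP dose. The undosed patients have no such date, so adding them leaves their data limit undefined unless a new rule is written.

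**The case against.** The strongest defence is that these are safety endpoints by the SAP's own classification. The question is whether IMP does harm, and a patient who never received it cannot show that harm. Measuring time from randomisation in dosed patients is also coherent; the SAP does not contradict itself. Both studies are double-blind, so the decision not to dose should not depend on arm. Exclusion that is related to prognosis but not to arm mainly changes the population studied and not the contrast.

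Most of this stands as a limit on size. It does not justify the choice. It gives no reason for grouping a randomised survival comparison by treatment received, nor for leaving out deaths that the endpoint definition includes.

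Stronger readings are tempting, and the SAP does not support them:

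- A reader might infer that the randomised comparison is broken. With 1.5% undosed under blinding, it is departed from, not broken.
- A reader might infer that the undosed patients are those who deteriorated early. The SAP gives no reasons for non-dosing.
- A reader might infer that grouping by treatment received moves patients between arms. The SAP reports no patient who received the wrong treatment.
- A reader might express the five undosed POLAR-M patients as a share of expected deaths and treat it as an upper bound. That needs a median OS which the SAP does not give. Each hazard ratio also compares two of the three arms, and Section 2.5 limits follow-up to 12 months, so a share of all deaths to data cut-off bounds nothing.

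**Conclusion.** The point holds as a minor one. Through the Section 6 default, PFS, OS and DFS are analysed in dosed patients by treatment received although they are timed from randomisation. This is a stated rule, not a detail left to the protocol. It leaves out 4 of 301 patients in POLAR-A and 5 of 290 in POLAR-M.

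The likely effect on the hazard ratios is small, and it is clearest for OS. The extreme OS figures in the working require every undosed POLAR-M patient to be in one arm with the same outcome, and nothing in the SAP suggests that. The conclusion that PFS and DFS may barely change rests on the assumption that undosed patients lack radiologic assessments.

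**What to change.** In each of Sections 6.10 to 6.12, add a statement such as: the analysis includes all randomised patients (ITT) according to assigned treatment; the same analysis in the safety set is a sensitivity analysis.

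For these endpoints, state the 12-month data limit of Section 2.5 from randomisation, or at least do so for patients who were never dosed. Leave the safety set in place for adverse events and laboratory data.

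The cost is a sentence in each section, a short cut-off rule and one extra sensitivity run per endpoint. The ITT set is already defined. Section 1 says the SAP is finalised before the blind is broken, so the change can be made without knowledge of results.
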